Study Design	
This is a prospective, open-label Phase 1/2 study to evaluate copper Cu 64 PSMA I&T injection for PET/CT imaging in patients with recurrent metastatic prostate cancer after radical prostatectomy or radiation therapy.
 
Phase 1
 
The Phase 1 portion of the study will include a total of 12 patients with metastatic prostate cancer. Patients will be randomized into three groups of four patients. Patients in each group will receive a single intravenous dose of 5, 7, or 9 mCi of copper Cu 64 PSMA I&T. Whole-body PET/CT images will be acquired at 1 hour <math>\pm</math> 15 minutes, 4 hours <math>\pm</math> 0.5 hours, and 24 hours <math>\pm</math> 2.0 hours post-injection to determine radiation absorbed dose estimates.
 
The 1 hour and 4-hour PET/CT images will be evaluated independently by three readers blinded to all patient information and dose administered to assess the quality of the images (24 PET/CT image sets total). The assessments will be used to determine an acceptable dose to be administered for the Phase 2 study.
 
Phase 2
 
The Phase 2 portion of the study will include a separate group of 26 patients with metastatic prostate cancer. Each patient will be administered the same intravenous dose of copper Cu 64 PSMA I&T injection determined in the Phase 1 study. PET/CT images will be acquired for all patients at 1 hour <math>\pm</math> 15 minutes and 4 hours <math>\pm</math> 30 minutes post copper Cu 64 PSMA I&T injection.
 
The PET/CT images will be interpreted independently by three readers blinded to all patient information. Each patient study will be assessed and scored for the detection of prostate cancer. Specifically, each reader will categorize images as "Disease" or "No Disease" based only on tumor

	
uptake of copper Cu 64 PSMA-I&T in each of the four regions: 1) prostate bed or prostate gland, 2) lymph nodes (pelvic and extra pelvic), 3) bone, and 4) viscera/soft tissue. Analysis of the reads will be used for determination of the CLR and CDR for 1 hour and 4-hour post-injection imaging of copper Cu 64 PSMA I&T PET/CT by comparison to the Composite Reference Standard.

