Study Population	
The study will include patients with metastatic proven prostate adenocarcinoma.
 
Phase 1: Total of 12 patients.
 
Inclusion Criteria:
 

1. Patients with histologically proven prostate adenocarcinoma.

2. Prior radical prostatectomy or radiation therapy with curative intent.

3. Recurrence of disease, defined as:

a. Prior Radical Prostatectomy: PSA > 0.2 ng/mL, or

b. Prior Radiation Therapy: 2 ng/mL rise in PSA over post-treatment nadir.

4. Patients with at least one extraprostatic site of disease suspected based on prior imaging or diagnosed by biopsy.

5. Age greater than or equal to 18 years.

6. Able to understand and provide signed written informed consent.

 
Exclusion Criteria:
 

1. Body weight greater than 350 lb. (158 kg).

2. Investigational therapy within the past 30 days.

3. Creatinine clearance (ClCr) less than 30 mL/min.

4. Participants who are capable of fathering a child and who are unwilling to take precautions to prevent pregnancy.

 
Phase 2: Total of 26 patients.
 
Inclusion Criteria:
 

1. Patients with histologically proven prostate adenocarcinoma.

2. Prior radical prostatectomy or radiation therapy with curative intent.

3. Recurrence of disease defined as:

a. Prior Radical Prostatectomy: PSA > 0.2 ng/mL, or

	
b. Prior Radiation Therapy: 2 ng/mL rise in PSA over post-treatment nadir
 
4. Patients with at least one extraprostatic site of disease suspected based on prior imaging or diagnosed by biopsy.
 
5. Age greater than or equal to 18 years.
 
6. Able to understand and provide signed written informed consent.
 
Exclusion Criteria:
 

1. Androgen deprivation therapy (ADT) or other therapies targeting the androgen pathway unless subject has a rising PSA level.

2. Body weight greater than 350 lb (158 kg).

3. Investigational therapy within the past 30 days.

4. Creatinine clearance (ClCr) less than 30 mL/min.

5. Participants who are capable of fathering a child and who are unwilling to take precautions to prevent pregnancy.

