	
Baseline Assessments:
 
Routine clinical chemistry, hematology, and urinalysis will be obtained for all patients prior to dosing. PSA will also be obtained for all patients prior to dosing.
 
Medical history and physical examination will be performed prior to dosing. This will include information on the history of the prostate cancer. Concomitant medication history will also be obtained.
 
Imaging Procedure:
 
All patients will undergo PET/CT imaging at 1 hour <math>\pm</math> 15 minutes and 4 hours <math>\pm</math> 30 minutes following copper Cu 64 PSMA I&T injection using the dose determined in Phase 1. The 1 hour and 4-hour images will be independently read by three experienced blinded readers for the detection of prostate cancer. Specifically, each reader will categorize images as “Disease” or “No Disease” based only on tumor uptake of copper Cu 64 PSMA-I&T in each of the four regions: 1) prostate bed or prostate gland, 2) lymph nodes (pelvic and extra pelvic), 3) bone, and 4) viscera/soft tissue.
 
Efficacy Analysis:
 
Composite Reference Standard
 
All patients will undergo an efficacy assessment based on copper Cu 64 PSMA I&T PET/CT results and the results of clinical presentation for evaluation against the Composite Reference Standard.
 
The Composite Reference Standard is defined as follows:
 

1. Local histopathology obtained from prostate cancer surgery or biopsy obtained within 60 days before or following copper Cu 64 PSMA I&T PET/CT, or

2. If histopathology is not available, anatomical correlation of conventional image findings (e.g., targeted MRI or CT or any FDA-approved PET PSMA agent) that are acquired prior to locoregional or systemic treatment and within 60 days before or following copper Cu 64 PSMA I&T PET/CT

 
Safety Assessments:
 
All patients will be followed for adverse events for 24 hours post-injection. Severity of adverse events will be assessed independently by the Investigators and graded using the National Cancer Institute Common Terminology Criteria for Adverse Events version 5.0, in which Grades 1, 2, 3, 4, and 5 describe adverse events as mild, moderate, severe or medically significant but not life-threatening, life-threatening, and death related to the adverse event, respectively.

--	---

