	
1. To determine the region-level correct localization rate (CLR) of copper Cu 64 PSMA I&T injection PET/CT imaging for the detection of recurrent metastatic prostate cancer at 1- and 4-hours post-injection. The CLR is defined as the percentage of regions containing at least one true PET positive lesion, with exactly localized correspondence between PET/CT imaging and the Composite Reference Standard regardless of any co-existent false positive findings, within the same region, out of all regions containing at least one PET positive finding.
 
2. To determine the patient-level correct detection rate (CDR) of copper Cu 64 PSMA I&T injection PET/CT imaging for the detection of recurrent metastatic prostate cancer at 1 hour and 4 hours post-injection. The CDR is defined as the percentage of patients who have a least one true PET positive lesion with exactly localized correspondence between PET imaging and the Composite Reference Standard regardless of any co-existent false positive findings, out of all patients who are scanned
 
Since all patients enrolled in the study will have disease, the CLR is a measure of the sensitivity of the copper Cu 64 PSMA I&T injection scan. Current methods have a CLR of 60%; thus, the hypothesis to be tested in the Phase 2 portion of the study is: H0: <math>\pi_C = \pi_0</math> versus HA: <math>\pi_C > \pi_0</math> where <math>\pi_C</math> is the CLR for copper Cu 64 PSMA I&T injection and <math>\pi_0</math> is the CLR from the literature (estimated to be 60%).
 
This hypothesis will be tested using an exact one-sample binomial test with a one-sided <math>\alpha=0.025</math>.
 
Secondary Objective:
 
The secondary objective for the Phase 2 study is to compare the diagnostic quality of PET/CT images obtained at 1 hour and 4 hours post copper Cu 64 PSMA I&T injection.
 
Safety Endpoint:
 
To assess the safety of copper Cu 64 PSMA I&T injection in patients with recurrent prostate cancer. Safety will be assessed by monitoring adverse events, clinical chemistry, hematology, urinalysis, ECG, and vital signs.
 
Analysis Populations:
 
Several analysis populations of patients are defined, which may provide a more complete description of the collected data, provide a logical mechanism for grouping and listing results based on an applied analysis, and/or allow appropriate stratification of various analyses.
 
1. The Enrolled Patient Population (EPP) represents patients who sign an Informed Consent Form and have baseline data.

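### Does the mention of clinical presentation in the Phase 2 efficacy paragraph bring an undefined input into CLR and CDR?

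*Combined protocol and SAP*

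**What the plan says.** All the places below are in the Protocol Synopsis.

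- **Efficacy Analysis (Phase 2 Study Procedures).** Under the sub-heading for the Composite Reference Standard, an opening sentence rests the assessment on "PET/CT results and the results of clinical presentation for evaluation against the Composite Reference Standard". The definition of the standard follows directly and has two items. The first is local histopathology within 60 days either side of the scan. The second begins "If histopathology is not available, anatomical correlation of conventional image findings", with a 60-day window and the condition that the images precede treatment.
- **Study Design, Phase 2.** The images are "interpreted independently by three readers blinded to all patient information". The same row then states: "Analysis of the reads will be used for determination of the CLR and CDR for 1 hour and 4-hour post-injection imaging", and names the Composite Reference Standard as the comparator.
- **Imaging Procedure (Phase 2 Study Procedures).** The read rule is that "each reader will categorize images as “Disease” or “No Disease” based only on tumor uptake of copper Cu 64" PSMA I&T, in each of four regions.
- **Study Objectives and Primary Efficacy Endpoints.** CLR and CDR are each defined twice. Each time the comparison is between PET (or PET/CT) and the Composite Reference Standard, and the two must agree on location.
- **Study Population and Primary Efficacy Endpoints.** Phase 2 patients must have PSA-defined recurrence and qualify as "Patients with at least one extraprostatic site of disease suspected based on prior imaging or diagnosed by biopsy". The endpoint text reasons from the premise "Since all patients enrolled in the study will have disease".

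**The concern.** The phrase fits neither side of the comparison. On the PET side it conflicts with readers who see no patient information and judge uptake alone. On the reference side it adds a third kind of evidence to a standard that lists two.

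The worry is sharper because of who is enrolled. Every Phase 2 patient has a rising or elevated PSA and a suspected or biopsied extraprostatic site. Clinical presentation therefore points to disease in everyone and cannot separate a true from a false PET finding at a particular site. If it counted as confirmation, CLR and CDR would tend to rise above the rates the plan defines, and the exact test of CLR against 60% would reject too often. If it entered on the PET side, the rates would no longer describe the blinded read, and the direction of the effect could not be told from the text.

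**Working it through.** **Step 1: does any operative rule use clinical presentation?**

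| Rule | Where (Protocol Synopsis) | Inputs named | Clinical presentation used? |
|---|---|---|---|
| Blinded read | Study Design; Imaging Procedure | Tracer uptake in four regions | No |
| Reference standard | Efficacy Analysis | Histopathology; otherwise conventional imaging | No |
| CLR | Study Objectives; Primary Efficacy Endpoints | PET/CT against the standard, location matched | No |
| CDR | Study Objectives; Primary Efficacy Endpoints | PET against the standard, location matched | No |
| Derivation of both rates | Study Design | The reads against the standard | No |
| Opening sentence | Efficacy Analysis | PET/CT results and clinical presentation | Named, with no scoring rule |

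The five rules that produce a number agree with one another. The sixth entry is an introduction: it does not say who scores clinical presentation, on what scale or at what step. History, physical examination and PSA are collected at baseline, but nothing carries them into an endpoint.

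**Step 2: can the phrase be made to work as an input?** Suppose patient-level clinical presentation did confirm a PET finding. Because eligibility gives it to every patient, every PET-positive region would be confirmed. With 60% of regions confirmed by the two-item standard and a share s of the rest credited clinically,

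apparent CLR = 0.60 + 0.40 × s,

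and s = 1 gives 1.00. The endpoint would be 100% by construction and the test against 60% would be empty. The location requirement in the CLR and CDR definitions rules this reading out, since symptoms or a PSA value do not identify a site. The reading that remains is that the phrase loosely refers to the clinical work-up (biopsy and imaging) that supplies the two items.

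**Step 3: what would partial crediting do, if it occurred?** The plan gives no figure to reproduce here.

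- From the Primary Efficacy Endpoints: null CLR 60%, exact one-sample binomial test, one-sided alpha 0.025.
- From the Study Design: 26 patients and four regions.
- Assumed: the number of PET-positive regions n, taken as 26, 52 or 104 (one, two or four per patient, for one reader at one time point); independence between regions; s of 10% or 25%; and that the 60% benchmark was scored by the same two-item standard.

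The critical value is the smallest r with P(X ≥ r | n, 0.60) ≤ 0.025. The apparent CLR is 0.60 + 0.40 × 0.10 = 0.64, or 0.60 + 0.40 × 0.25 = 0.70.

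| n | Critical value r | P(reject), s = 0 | s = 10% | s = 25% |
|---|---|---|---|---|
| 26 | 21 (80.8%) | 2.1% | 5.3% | 16.3% |
| 52 | 39 (75.0%) | 1.7% | 6.3% | 26.7% |
| 104 | 73 (70.2%) | 2.0% | 11.2% | 53.1% |

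Starting from about 60% confirmed (16, 31 and 62 regions), rejection needs 21 − 16 = 5, 39 − 31 = 8 or 73 − 62 = 11 further regions. That is 5/10 = 50%, 8/21 = 38% or 11/42 = 26% of the unconfirmed ones.

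The arithmetic is sound, but only the s = 0 column follows from the plan. The row for 104 also requires all four regions to be PET-positive in every patient.

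**The case for a change.** The strongest case for a change is that this sentence introduces the method for both primary efficacy endpoints, that the trial is open-label, and that the conflict is on the page whatever its origin. Clear definitions elsewhere make the sentence easy to correct; they do not make it correct. If it means the standard-of-care work-up, qualifying work-up is already inside the two items and anything else lies outside the standard. Rewording one sentence adds no patient, scan or read. A related point is that the available text does not say how lesion positions are matched.

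Part of this stands. The phrase is undefined in the available text and out of step with the rest of the synopsis, and removing or defining it would be reasonable tidying at the next revision. What does not stand is that the endpoints have competing inputs: one introductory phrase without a scoring rule does not displace definitions that are each stated twice and agree with the derivation sentence. The blinding rules also govern the reads, whereas the sentence describes the later assessment, so no breach of blinding is shown. Lesion matching is a separate matter of operational detail that may sit in a reader manual; the Phase 1 procedures already cite one for the readers' measurements.

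**Conclusion.** The concern does not call for a change. The phrase is a minor wording inconsistency in an introductory sentence. The definitions of CLR, CDR, the blinded read and the Composite Reference Standard are consistent, and they determine the result without it. The demonstrated effect on CLR, CDR and the type I error of the CLR test is therefore nil. The larger rejection probabilities need a crediting step that the plan does not contain and that its location requirement excludes.

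This rests on two assumptions: that analysts apply the stated endpoint definitions, and that no section beyond the synopsis gives clinical presentation a scoring role. Only the abbreviations and the synopsis were available, so a fuller definition elsewhere cannot be ruled out. A section that did credit regions on clinical grounds would reopen the question.

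### Without histology, an FDA-approved PSMA PET can be the only reference for a Cu-64 PSMA PET finding, so shared false positives may raise the tested CLR; the reference rules also leave smaller gaps around treatment

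*Combined protocol and SAP*

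**What the plan says.** The Composite Reference Standard is defined in the Protocol Synopsis, Phase 2 Study Procedures, Efficacy Analysis. It has two items.

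- Item 1 is histology: "Local histopathology obtained from prostate cancer surgery or biopsy obtained within 60 days before or following" the Cu-64 PET/CT. It carries no condition about treatment.
- Item 2 is the fallback: "If histopathology is not available, anatomical correlation of conventional image findings". The examples given are "MRI or CT or any FDA-approved PET PSMA agent) that are acquired prior to locoregional or systemic treatment and within 60 days" before or after the Cu-64 PET/CT.

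The reference feeds both primary efficacy endpoints. CLR counts regions with a PET lesion matched exactly to the reference, "out of all regions containing at least one PET positive finding". CDR counts patients with at least one such match among all patients scanned. Only CLR has a stated hypothesis test: exact binomial, one-sided 0.025, against a literature value introduced as "Current methods have a CLR of 60" per cent.

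Three Phase 2 eligibility criteria bear on this:

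- Inclusion criterion 4 admits "Patients with at least one extraprostatic site of disease suspected based on prior imaging or diagnosed by biopsy".
- Exclusion criterion 1 is "Androgen deprivation therapy (ADT) or other therapies targeting the androgen pathway unless subject has a rising PSA level".
- Exclusion criterion 3 is "Investigational therapy within the past 30 days".

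**The concern.** **Main point.** CLR is counted over PET-positive regions, so it behaves like a positive predictive value: every PET-positive region that the reference fails to confirm is a failure. A reference that shares the index test's errors turns some of those failures into successes. Item 2 permits such a reference, because another PSMA PET images the same target. Uptake that binds PSMA but is not cancer can appear on both scans and be scored as true. CDR is exposed in the same way, although it has no stated test.

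The scan that qualified the patient may also be the confirming scan. Criterion 4 admits men on prior imaging. A qualifying PSMA PET older than 60 days cannot be the reference, but nothing in the eligibility criteria or the reference definition stops one that meets item 2's limits.

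**Lesser point.** Item 2 requires the reference image to precede treatment, which protects images taken after the Cu-64 PET. It does not cover the order reference image, treatment, Cu-64 PET, all within 60 days. Item 1 has no treatment condition in either direction. Three effects follow:

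- A true lesion treated after the PET and then biopsied may read negative, which lowers CLR.
- A lesion treated after its reference image may lose uptake before the Cu-64 PET. This can lower CDR if no other lesion in that patient is confirmed.
- Rarely, a specimen taken before the PET may validate later uptake in the resected region.

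The Phase 2 exclusions do not close these gaps. Exclusion 3 covers investigational therapy only, for 30 days against a 60-day reference window. Exclusion 1 admits men on ADT whose PSA is rising.

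**Working it through.** **Reading the definition.** Item 2 joins MRI, CT and PSMA PET by 'or' and names no second modality. One might read anatomical correlation as requiring a CT or MRI correlate, but PSMA PET is itself listed among the image findings to be correlated. As written, a PSMA PET alone is enough.

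**Size.** The synopsis gives no target CLR, power or expected number of PET-positive regions for Phase 2, so there is no figure of the plan's to reproduce. What follows is an illustration.

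From the documents: null CLR 0.60, one-sided alpha 0.025, exact binomial test, 26 patients.

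Assumed: 26 independent PET-positive regions, one per patient.

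Cut-off: P(X ≥ 20) = 0.0559 and P(X ≥ 21) = 0.0214 for X ~ Bin(26, 0.60). The test needs 21 of 26, with actual size 0.021.

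*Shared false positives.* Take a true CLR of 0.60. Let f be the share of false-positive regions judged by PSMA PET alone, and g the chance that the second scan reproduces a false positive. Then

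measured CLR = 0.60 + 0.40 × f × g,

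and false success is P(Bin(n, measured CLR) ≥ cut-off). The columns for 20 and 40 regions use cut-offs 17 (size 0.016) and 31 (size 0.016).

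| f | g | Measured CLR | 26 regions | 20 regions | 40 regions |
|---|---|---|---|---|---|
| 0.2 | 0.2 | 0.616 | 0.031 | 0.022 | 0.025 |
| 0.3 | 0.3 | 0.636 | 0.049 | 0.034 | 0.045 |
| 0.5 | 0.5 | 0.700 | 0.163 | 0.107 | 0.196 |
| 0.8 | 0.5 | 0.760 | 0.381 | 0.257 | 0.498 |

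The effect is small when f and g are low. It becomes large only when PSMA PET is a main source of confirmation.

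*Histology after treatment.* Take a true CLR of 0.85, again assumed. Let s be the share of true-positive regions whose histology follows treatment given after the Cu-64 PET, and r the share of those that read negative. Then measured CLR = 0.85 × (1 − s × r). With s = 0 the chance of passing is P(Bin(26, 0.85) ≥ 21) = 0.815. With s = 0.10:

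| r | Measured CLR | Chance of passing |
|---|---|---|
| 0.10 | 0.8415 | 0.779 |
| 0.25 | 0.8288 | 0.721 |
| 0.50 | 0.8075 | 0.616 |

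*Cost of refusing PSMA PET alone.* With true CLR 0.85 and 26 regions, suppose 10% or 20% of true positives can be confirmed only by PSMA PET. Counted as failures, they bring CLR to 0.85 × 0.90 = 0.765 or 0.85 × 0.80 = 0.680. The chance of reaching 21 of 26 falls from 0.815 to 0.404 or 0.115.

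**The case against.** The strongest reply is that PSMA PET is in the reference for good reason: it can correctly confirm true lesions that CT or MRI miss. Removing it would label true positives as failures, and the last calculation above shows how costly that could be. This stands. It is why the composite should remain primary, and why an analysis without PSMA-PET-only confirmation can only be a lower bound.

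The 60% comparator may also rest on a similar composite, in which case part of the inflation would cancel. The documents do not give the reference standard behind that figure, so cancellation can be neither assumed nor ruled out.

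On treatment, a reader might infer that the gap in item 2 also inflates CLR, because uptake after treatment is credited to an earlier positive image. The documents do not support that. CLR requires exact localization, and uptake that persists where disease was shown within 60 days is most plausibly residual disease, a true positive. If the earlier image was itself false, that is the shared-error problem and not a treatment problem. The only upward route through treatment is the resected-region case. It is narrow: it needs an excision within 60 days before the PET and then new false uptake at the same site.

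A reader might also infer that the eligibility criteria and the reference definition contradict each other over men on ADT. They do not. Every patient has had prostatectomy or radiotherapy, so treatment in item 2 can only sensibly mean new treatment, and continuing ADT fits that reading. A clarifying phrase is enough.

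Finally, only the synopsis was available for this review. Reference rules or reporting by type of reference may appear in sections not seen.

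**Conclusion.** The main point holds as a weakness in the design of the reference standard. As written, a same-target PSMA PET, possibly the qualifying scan, can be the sole confirmation of a region in the tested endpoint. Shared false positives can then count as correct localizations and may raise CLR.

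That this happens to a material degree is not established. In the illustration, false success moves from 0.021 to 0.031 at f = g = 0.2, to 0.049 at f = g = 0.3 and to 0.163 at f = g = 0.5. The values of f and g, the true CLR and the 26 independent regions are all assumptions. It would go too far to say that CLR will be biased upward against 60%: the net direction depends on how many true lesions only PSMA PET can confirm and on the reference behind the 60%.

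The treatment gaps are real but secondary. Their main effects are downward, on CLR through histology taken after treatment and possibly on CDR through lost uptake.

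This should be changed, as a cheap improvement. Confidence is medium.

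**What to change.** Settle the following before the reference reads; reference rules chosen after results are seen would carry little weight.

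1. Keep the composite as the primary reference.
2. Report CLR and CDR by type of reference: histology, CT/MRI, and PSMA PET only.
3. Pre-specify a sensitivity analysis in which PSMA PET alone does not confirm a finding, and present it as a conservative lower bound.
4. Add one rule to both items about which references count, not about patient care. A reference is valid for a region only if no locoregional treatment of that region and no new systemic treatment fell between the reference and the Cu-64 PET, in either order. A surgical specimen taken after the PET remains valid. One taken before it does not validate later uptake in the resected region. Continuing ADT is not new treatment.

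The cost is a few sentences, one table and one sensitivity analysis, with no extra patients or scans. There are three downsides. Some references become unusable, which may lower CDR because its denominator is all patients scanned. Estimates by type of reference will be imprecise with 26 patients. The sensitivity analysis can count true positives as failures, so falling short of 60% there would not by itself overturn the primary result.
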